### **I. PURPOSE OF THE STUDY AND BACKGROUND**

#### **Purpose of the study.**

[figure not shown]
The aim of this study is to examine the effect of parasternal intercostal nerve blocks with extended-release liposome bupivacaine (Exparel®) on pain control in patients undergoing non-emergent cardiac surgery in a prospective randomized controlled trial.

#### **Background.**

Inadequate post-operative pain control is a significant problem faced by many patients undergoing cardiac, thoracic and abdominal surgery. Barriers to adequate pain control include unwillingness or inability of the patient to request for pain medication, inability of nursing to reach the patient in a timely manner and hesitance of health care providers to prescribe and reluctance of nurses to administer pain medication. Poorly controlled pain has been shown to lead to various physiologic changes including tachycardia and hypertension, which causes increased myocardial oxygen demand. In addition, inadequate pain control results in splinting and decreased mobilization, increased morbidity and longer lengths of stay.

Opioids along with non-opioid and nonsteroidal anti-inflammatory agents are the mainstays of treatment for post-operative pain in adult cardiac patients. However, the doses of opioid often required can result in respiratory depression, delay of extubation, nausea, vomiting, delirium, slowing of gastrointestinal motility and hypotension from peripheral vasodilatation. For these reasons, a better method of pain management would be valuable. Neuraxial anesthesia (e.g. thoracic epidural anesthesia, spinal anesthesia and paravertebral blocks) has shown benefits, yet remains controversial and not widely accepted in cardiac surgery due to concerns regarding associated hypotension and paresthesias, as well as potential development of epidural abscess or epidural hematoma following anticoagulation.

[figure not shown]
Parasternal intercostal blocks using local anesthetics have been shown to provide improved post-operative pain control and decreased opiate requirements with less potential complications. The sensory innervation of the thorax is provided by the 2nd through 6th intercostal nerves. The intercostal nerves terminate in anterior cutaneous branches, which divide into medial and lateral branches, providing innervation to the anterior chest wall (Fig.1). A parasternal intercostal nerve block targets the anterior intercostal nerves just lateral to the sternum (Fig. 2a). Local anesthetic is injected along the undersurface of each rib, infiltrating the space where the intercostal nerve travels (Fig. 2b). By doing this prior to sternal closure, the surgeon is able to perform the block under direct visualization of the nerves and rib interspaces.

Reproduced from. Gray, Henry. *Diagram of the course and branches of a typical intercostal nerve.* 1918. Illustration. *Anatomy of the Human Body*, 20th ed. By Henry Gray. Philadelphia, PA : Lea & Fbiger, 1918.

**Figure 1.** Saggital view of intercostal space. The intercostal nerve gives off the lateral and anterior cutaneous nerves. The anterior cutaneous nerve penetrates through the intercostal muscles just lateral to the sternum before dividing into medial and lateral branches. These branches supply the anterior chest wall.

Images adapted from: (a) Singer, Raymond L. "Median sternotomy." Illustration. 12 Sept. 2012.

[figure not shown]

[http://www.heartlungdoc.com/heart/bypass/coronary\\_images/Sternotomy%20Diagram.jpg](http://www.heartlungdoc.com/heart/bypass/coronary_images/Sternotomy%20Diagram.jpg). Accessed 12 Sept. 2012. (b) "Intercostal nerve block." Illustration. <http://www.advancedorthopain.com/pain-procedures/images/interc1.jpg>. Accessed 21 Sept. 2012.

**Figure 2.** Parasternal intercostal nerve block. **(a)** Target injection sites are marked (X). Each intercostal space was infiltrated, 2 cm lateral to the sternal border, as well as the deep subcutaneous space around the mediastinal tubes. **(b)** Local anesthetic is injected along the undersurface of each rib, where the neurovascular bundle travels.

In a randomized-controlled trial (RCT) comparing parasternal nerve blocks using ropivacaine vs. placebo, Barr et al. showed a 30-50% reduction in pain scores and total opiate use. The differences between placebo and ropivacaine group were greatest over the first 12 hours post-op and subsequently diminished over the next 12 hours of observation. These benefits were extended over 72 hours with the addition of continuous local infusion of ropivacaine. Thus demonstrating that the efficacy of a parasternal nerve block is limited by the duration of action of the local anesthetic used. Bupivacaine is another long-acting local anesthetic (amide-type local anesthetic) that is routinely used for postsurgical anesthesia, yet the maximum duration of this drug is only 6-12 hours. We hypothesize that use of a longer-acting local anesthetic will potentiate the benefits of improved pain control and reduced opioid requirements.

Exparel® is a long-acting, extended-release liposome injection of bupivacaine that has been FDA-approved for “single-dose infiltration into the surgical site to produce postsurgical anesthesia”. Exparel® is a liquid suspension of spherical, microsomal liposomes (DepoFoam® drug delivery system) containing multiple aqueous chambers of encapsulated bupivacaine (Fig. 3). Bupivacaine is gradually released from the liposomes by diffusion as the unprotonated (uncharged) form of bupivacaine. This formulation allows for sustained release of bupivacaine at the site of injection without exposing patients to toxic plasma concentrations. In clinical trials, Depofoam® bupivacaine has shown duration of action up to 72 to 96 hours, while peak plasma bupivacaine concentration (0.4 to 1.4 µg/ml) remained well below the reported toxic plasma concentration (2-4 µg/ml). Randomized clinical trials (RCT) comparing Exparel to bupivacaine and placebo in various surgeries (e.g. hemorrhoidectomy, bunionectomy, inguinal hernia repair, total knee replacement) have shown improved outcomes of pain control and decreased narcotic requirements. In RCTs with patients undergoing hemorrhoidectomies, benefits from Exparel® were more substantial from 12-72 hours with a 47% reduction in cumulative pain score and 66% relative reduction in opioid consumption compared to bupivacaine.

**Figure 3.** Cross-sectional diagram of DepoFoam® drug delivery system containing aqueous chambers filled with Bupivacaine.

Reproduced from Chahar P, Cummings KC. *Liposomal bupivacaine: a review of a new bupivacaine formulation.* J Pain Research. 2012.

To compare differences in pain control, we will use a number of validated pain assessment tools. These include the adult nonverbal pain scale (NVPS), numerical rating scale (NRS) and brief pain inventory (BPI) (see Appendix II and III). The NVPS has been adopted by the cardiovascular ICU (CVICU) for assessing pain in critically-ill, intubated patients. It includes assessments of the patient’s face, body movements, muscle tension and vital signs to determine a total score ranging from 0 to 10. It has been shown to exhibit high reliability and inter-rater agreement, as well as increase patient and staff satisfaction. The NRS is an 11-point scale ranging from 0, “no pain”, to 10, “the worst possible pain”, that is used by nursing staff for

assessing and documenting pain in extubated, alert patients. The scale has shown high sensitivity and simplicity. Moreover it is interval and allows for parametric analysis. The BPI consists of four questions rating pain severity and seven questions regarding impact of pain on daily function, allowing calculation of pain severity and interference indices for comparison. Studies have shown that BPI scores correlate with the number of days from surgery and decreasing analgesic requirements.

Exparel® is not currently FDA-approved for peripheral nerve blocks. There are two ongoing clinical trials studying the use of Exparel® for femoral nerve blocks. However, Exparel® has not previously been studied for our specific application. Thus, we are conducting this study to evaluate the efficacy and safety of Exparel® in parasternal nerve blocks in cardiac surgery patients. Successful use of Exparel® for parasternal intercostal nerve blocks may revolutionize the management of post-cardiac surgery pain. Optimal pain control and reduced opioid doses would enable earlier extubation and mobilization, less opioid-associated morbidity and shorter ICU and total hospital lengths of stay.

**Hypothesis:** We hypothesize that administration of Exparel® in parasternal nerve blocks will provide improved pain control and decreased narcotic use in the adult post-operative cardiac surgery patient.

**Primary aim:** To determine if there is a statistically significant improvement in analgesia and decreased opioid requirements in the post-operative period.

**Secondary aim:** To look at differences in LOS (ICU and hospital), time to return of bowel function, and time to return to work or daily activities. We will also look at incidence of complications related to inadequate pain control and the incidence of adverse events.

## II. CHARACTERISTICS OF THE RESEARCH POPULATION

### Number of subjects.

The study will include 78 patients, 39 patients in the study drug arm and 39 patients in the control arm. Since there are two primary outcomes, we set the type I error at 0.025 for the power analysis. Based on results from a prior study by Barr et al., we assumed a baseline Numerical Rating Scale (NRS) score for pain of 53.2 with standard deviation of 24.1 and a baseline cumulative morphine requirement over 24 hours of 23.2 mg with standard deviation of 8.3 mg. The proposed sample size was calculated to achieve 86% power to detect a 30% decrease in mean NRS scores at the 2.5% level of type I error (two-sided). This sample size also provides for a 98% power to detect a 30% decrease in total opioid consumption over the first 24 hours post-operatively. Note that we assumed the standard deviation decreases accordingly. A 5% drop out rate was included into the sample size calculation.

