**Withdrawal Criteria.**

Patients meeting these intra-operative and post-operative criteria will be withdrawn from the study because of the likelihood that these characteristics will independently affect primary and secondary study outcomes. However, primary and secondary outcomes will still be collected for these patients and results included in an “intention-to-treat” analysis.

- Post-operative intubation longer than 16 hours.
- Cardiopulmonary bypass time  $> 3$  hours or aortic cross-clamp time  $> 120$  minutes.
- Return to OR during hospital admission.

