### Randomization and Blinding

Patients will be randomized on the day of surgery to either placebo or treatment group. The subjects will be randomized in blocks of 4 to ensure a 1:1 ratio of placebo to treatment groups.

- Placebo: 0.9% normal saline
- Treatment group: 0.53% Exparel®

A randomization sheet will be generated by the study pharmacist, listing the randomization schedule in sequence for each block. The study pharmacist will have control of the randomization sheet. At the time of randomization, he will go to the next available row to determine which medication to dispense. The randomization sheet will document each subject's number, initials, date of surgery and study arm (active or placebo).

The study pharmacist will hold the key identifying which study group corresponds with which letter. In order to maintain blinding of the study investigators, the pharmacist will not reveal the subject's group assignment and data collection will be done according to the subject number. At quarterly intervals during the trial, the study pharmacist will reveal the blinding to the Independent Data/Safety Monitor (DSM) only. This will enable the Independent DSM to capture for any alarming trends in adverse events or serious adverse events as they are occurring. At completion of data collection and analysis for the entire study, the pharmacist will provide the study investigators with a copy of the report revealing which subject belonged to which study group.

The subjects will be blinded to their study arm and remain blinded for the entire duration of this study. Subjects who wish to know which drug they received (Exparel® or placebo), may contact the PI or co-PI and they will be informed of their study group following completion the study.

The study investigators, surgeon administering the medications, operating room staff and ICU/floor staff will all remain blinded. Only the pharmacist who will prepare and dispense the medication will be unblinded.

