### Statistical analysis

Descriptive statistics will be reported for each group. Means with standard deviation and 95% confidence intervals of the means will be reported for continuous variables and frequency and proportion distribution will be reported for categorical outcomes.

Student t-test (for normally distributed continuous variables) and Wilcoxon rank sum tests (for non-normally distributed variables) will be used to compare continuous outcomes such as AUC for adult NVPS/ NRS and opioid requirements between the two groups. For categorical outcomes, chi-square tests will be used to compare differences between the two groups. If some cell counts are small and the asymptotic tests are not reliable, then exact methods will be used. A general linear regression model for NRS scores will be applied to show the main effect for the treatment group, adjusting for covariates. Regression analysis will also be applied to opioid requirements. For the binary outcome of whether a patient has reached his/her maximum allowed dose of opioid, logistic regression models will be applied. For the opioid requirement outcome, patients who have reached their maximum allowed dose of opioid will be treated as censored and a Tobit regression model will be applied. Since there are two primary outcomes, a type I error of 2.5% will be used. All the tests will be two-sided.

Survival analyses will be applied for time to event data, such as the lengths of stay and mean time to return of bowel function. Logrank tests will be applied for simple comparisons between the two groups. Cox proportional hazards models will be used to facilitate the inclusion of covariates in the regression analysis. Note that although no censoring of subjects are expected in the study (i.e. the lengths of stay and mean time to return of bowel function will be observed for each patient) and a general linear regression analysis may be applicable, our survival analysis approach enables us to estimate the survival curves and read the different rates at different time points from the curves.

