#### Self-audit

An internal self-auditing of the blinded data will be conducted by the PI and co-PI. The data evaluated by the PI and co-PI during self-audits will be in the blinded form. Subject groups will only be identified by the arbitrary letter assigned to them by the study pharmacist in order to protect the true identity of their group (placebo or Exparel®). An initial self-audit will be conducted after completion of the 1st patient participation. During this audit, the PI and co-PI will review and discuss:

- abnormal laboratory data
- cumulative pain scores
- cumulative opioid use
- secondary outcomes
- adverse events
- signed informed consents
- any need for revision of study methods and procedures or data collection forms

Also reviewed during self-audits will be any feedback from involved departments (including pharmacy, anesthesia and nursing) regarding adverse events or concerns related to the subjects' participation. These departments may contact the PI or co-PI with any concerns at any time during the study via telephone or email.

A repeat self-audit will be conducted after completion of the 3rd patient participation to evaluate effectiveness of any changes made to the study protocol and/or data collection forms. Another self-audit will occur following 50% completion of subject participation (39 patients).

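### With one pre-named test per primary outcome, Holm's procedure keeps the 5% bound of the fixed 2.5% rule and raises NRS power from 86% to 91–92% at 39 per arm (84% to 90% at 37), with no gain or loss if opioid use is unaffected

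*Combined protocol and SAP*

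**What the plan says.** All references are to the combined protocol and SAP.

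- **Alpha.** Number of subjects: "Since there are two primary outcomes, we set the type I error at 0.025 for the power analysis". Statistical analysis: "Since there are two primary outcomes, a type I error of 2.5% will be used". Tests are two-sided. No step-down rule or other passing-on of alpha appears.
- **Power.** Number of subjects gives 86% for a 30% decrease in NRS with 39 per arm. For the other outcome it says: "This sample size also provides for a 98% power to detect a 30% decrease in total opioid consumption over the first 24 hours post-operatively". On spread it adds: "Note that we assumed the standard deviation decreases accordingly". A 5% dropout is said to be included.
- **Analyses.** Data Analysis lists six NRS AUC intervals (0-12 to 0-72 hours) and nine opioid intervals (0-2 to 0-72 hours). Statistical analysis offers a t-test or Wilcoxon test, linear regression, a Tobit model for opioid use, and mixed models or GEE. It prefers GEE if those last two disagree, but does not say whether either replaces the AUC test. No NRS interval is named as primary. The 0-24 hour opioid interval appears only in the power statement.
- **Withdrawn patients.** Under Withdrawal Criteria, "primary and secondary outcomes will still be collected for these patients", and their results enter an intention-to-treat analysis.
- **Access to results.** Randomization and Blinding: "At completion of data collection and analysis for the entire study, the pharmacist will provide the study investigators with a copy of the report". In the self-audits the PI and co-PI review cumulative pain scores and opioid use, and "Subject groups will only be identified by the arbitrary letter assigned to them by the study pharmacist". Audits follow the 1st and 3rd patients and the 39th.

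**The concern.** A fixed 2.5% per outcome is a Bonferroni split. When one outcome succeeds, its 2.5% could pass to the other at no cost in family-wise error, but the plan lets it lapse. NRS is the weaker outcome (86% against 98%), so it is usually NRS that would benefit. The primary aim names better analgesia together with lower opioid requirements, so the chance of showing both matters.

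There is a precondition. Bonferroni and Holm both assume one p-value per outcome, fixed in advance. With six and nine intervals and several models, the plan does not supply that. Letter codes hide which drug is which, but not whether the groups differ, and a two-sided test needs only the latter. If the interval or test is chosen after letter-coded results are seen, neither rule assures 5%.

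**Working it through.** **Inputs (Number of subjects).** Control NRS mean 53.2, SD 24.1. Control 24-hour opioid mean 23.2 mg, SD 8.3 mg. Decrease 30% in both, with the treated SD also 30% lower. 39 per arm; after 5% loss, 39 × 0.95 ≈ 37. The documents give no correlation between the outcomes, so 0 to 0.6 is assumed.

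**1. Reproduce the stated power.** Standard error = √((s₁² + s₂²)/n).

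- NRS: difference 0.3 × 53.2 = 15.96; treated SD 0.7 × 24.1 = 16.87; SE = √((580.81 + 284.60)/39) = 4.71; ratio 15.96/4.71 = 3.39.
- Opioid: difference 0.3 × 23.2 = 6.96; treated SD 0.7 × 8.3 = 5.81; SE = √((68.89 + 33.76)/39) = 1.62; ratio 4.29.

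Power from the noncentral t distribution:

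| Analysed per arm | NRS at 2.5% | NRS at 5% | Opioid at 2.5% |
|---|---|---|---|
| 39 | 86.2% | 91.7% | 97.6% |
| 37 | 84.2% | 90.2% | 96.9% |

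The plan's 86% and 98% are reproduced at 39 per arm.

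**2. The 5% bound under Holm.** If both nulls are true, a false rejection needs the smaller p-value to be at most 0.025, which has probability at most 0.025 + 0.025 = 0.05. If one null is true, its p-value must be at most 0.05. Neither step uses the correlation. Simulation at 39 per arm agrees. With both null, family-wise error is 5.0%, 4.7% and 4.0% at correlations 0, 0.5 and 0.8, identical to the fixed rule. With one null it is 4.1–4.9%.

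**3. NRS power under Holm.** NRS is rejected if its p ≤ 0.025, or if its p lies between 0.025 and 0.05 and the opioid p ≤ 0.025. At zero correlation:

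- 39 per arm: 0.862 + (0.917 − 0.862) × 0.976 = 0.916.
- 37 per arm: 0.842 + (0.902 − 0.842) × 0.969 = 0.900.
- 39 per arm, opioid use unaffected: 0.862 + 0.055 × 0.025 = 0.863, a gain of about 0.1 point.

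Simulation (t-tests, bivariate normal data, 40,000 trials per setting, correlation 0 to 0.6):

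| Setting | Fixed 2.5% | Holm |
|---|---|---|
| NRS, 39 per arm | 86% | 91–92% |
| Both outcomes, 39 | 84–85% | 91% |
| NRS, 37 per arm | 84% | 90% |
| Both outcomes, 37 | 82–83% | 89% |

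At a correlation of 0.8 with 39 per arm, NRS power under Holm is 91.2%.

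**4. Sensitivity of NRS power.**

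| Change from the plan's assumptions | 39 per arm | 37 per arm |
|---|---|---|
| Opioid decrease 20%, Holm | 88–90% | 86–88% |
| Opioid decrease 10%, Holm | 87% | 84–85% |
| No opioid effect, Holm | 86% | 84% |
| Constant SD, fixed → Holm | 73–74% → 81% | 71% → 79% |
| Wilcoxon for both, normal data, fixed → Holm | 84% → 89–90% | 81% → 87–88% |

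With Tobit for opioid use and an assumed 10–50% of controls censored (the documents give no rate), the NRS gain is about 4–6 points. Opioid power at 37 per arm then falls from 97% to 92% as censoring rises.

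The documents give no SD for any NRS AUC. The planning ratio of SD to mean is 24.1/53.2 = 45%. At 39 per arm, NRS power at 2.5% and at 5% (the most Holm could reach) is 94% and 97% for a ratio of 40%, 78% and 86% for 50%, and 69% and 79% for 55%.

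**5. The interval mismatch.** Trials in which Holm declares NRS significant but the fixed rule does not: 0.916 − 0.862 ≈ 5% at 39 per arm. In these the 97.5% interval includes zero. The expected NRS half-width is 10.8 at 97.5% against 9.4 at 95%.

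**The case against.** The fixed rule is valid, is applied consistently to power and analysis, and its stated powers reproduce. The main objections are these.

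- **At least one success.** Holm's first step is the Bonferroni step, so the chance that at least one outcome is significant is the same under both rules (98% to nearly 100% at 39 per arm with both effects present). This stands: Holm helps only the second outcome.
- **The success criterion is not stated.** If both outcomes were required, each could be tested at 5% without a split, and power for both would be about the same as under Holm (90.9% against 90.8% at correlation 0.3). The alpha split points to the either-outcome reading. Holm protects that reading and loses almost nothing on the other.
- **The headline is the favourable case.** It needs 39 analysed per arm, a 30% opioid decrease, a shrinking SD and t-tests. This is fair, and power should be restated with those conditions. Follow-up of withdrawn patients makes 39 possible, but 37 is the safer figure.
- **Naming one test is a separate gap.** True: the present rule needs it too, so it should not count as a cost or merit of Holm.
- **Early audits.** One or three patients cannot guide a choice of analysis, and the plan describes no between-group test at audits. The 39-patient audit is the one that matters.
- **Matching intervals.** Preferring a rule with simple simultaneous intervals is defensible. The 5% mismatch is the price of the gain.

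**Conclusion.** The point holds as a cheap improvement, not as an error in the plan. Once one p-value per primary outcome is fixed in advance, Holm cannot reject less than the fixed rule and keeps the same 5% bound.

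Under the plan's assumptions the gain is 5–6 points of NRS power and 6–7 points of power for both outcomes. It rests mainly on a real opioid effect: 1–4 points at a 20% decrease, about 1 point or less at 10%, and nothing material if there is none. The level of power, as distinct from the gain, also depends on the shrinking SD and on the unstated SD of the chosen AUC. The family-wise bound and the dominance over the fixed rule depend on none of these.

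**What to change.** State in Number of subjects and in Statistical analysis:

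> Primary pain outcome: NRS AUC over [one listed interval]. Primary opioid outcome: total opioid use over 0-24 hours. Each is compared by one named test: [test] for NRS and [test] for opioid use; the Tobit model is [the primary / a supportive] opioid analysis. The two p-values are tested by Holm at two-sided 5%: the smaller against 0.025 and, if significant, the other against 0.05. All other intervals and models are supportive. 97.5% confidence intervals are reported for both treatment differences.

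Restate NRS power for the named tests, with the assumed opioid effect, shrinking and constant SD, 39 and 37 analysed per arm, and the SD of the chosen AUC.

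Settle this before anyone who sets or runs the analysis sees outcomes by group, including letter-coded groups. The simplest deadline is before the first self-audit; the critical one is before the 39-patient audit. If by-group outcomes have already been seen, date the change and have it decided by a statistician who has not seen them.

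The cost is a few sentences and no added patients or data. The one statistical cost is that Holm has no equally simple matching simultaneous intervals, so the report should explain an NRS result that is significant while its 97.5% interval includes zero.

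### The stated 86% and 98% power match a t-test on all 39 patients per arm; with the 5% dropout said to be included, the planned t-test gives about 84% and 97%.

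*Combined protocol and SAP*

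**What the plan says.** Section II, Number of subjects, sets the size: "The study will include 78 patients, 39 patients in the study drug arm and 39 patients in the control arm". The significance level is split between the two primary outcomes: "Since there are two primary outcomes, we set the type I error at 0.025 for the power analysis". For pain, "we assumed a baseline Numerical Rating Scale (NRS) score for pain of 53.2 with standard deviation of 24.1"; for opioids, the plan takes "a baseline cumulative morphine requirement over 24 hours of 23.2 mg with standard deviation of 8.3 mg".

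The main claim is "The proposed sample size was calculated to achieve 86% power to detect a 30% decrease in mean NRS scores at the 2.5% level", two-sided. The same sample size is credited with 98% power for a 30% fall in opioid use over the first 24 hours. Two remarks close the section: "Note that we assumed the standard deviation decreases accordingly" and "A 5% drop out rate was included into the sample size calculation".

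The section does not name the formula or software. It gives no number of evaluable patients per arm, and does not say whether the powers refer to patients enrolled or patients analysed.

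Two other places matter. Statistical analysis (Section III) plans a Student t-test for normally distributed continuous outcomes and a Wilcoxon rank sum test otherwise. Withdrawal Criteria (Section II) says that outcomes are still collected for patients who meet those criteria and enter an intention-to-treat analysis.

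**The concern.** A reader of the sample size section will take 86% and 98% as the power that remains once 5% of patients are lost. The printed figures coincide instead with the planned t-test when nobody is lost. If that is how they were obtained, the plan states a power and a dropout allowance that 78 patients do not deliver together under the planned test. What is at stake is the accuracy of a stated design figure. The larger share of the gap falls on NRS, the outcome with the lower power.

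**Working it through.** **Inputs, all from Number of subjects**

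- Control NRS: mean 53.2, SD 24.1. Control 24-hour opioid use: mean 23.2 mg, SD 8.3 mg.
- Differences: 0.30 × 53.2 = 15.96; 0.30 × 23.2 = 6.96 mg.
- Treatment-arm SD, reading the SD remark as a 30% fall: 0.7 × 24.1 = 16.87; 0.7 × 8.3 = 5.81 mg.
- Two-sided level 0.025 for each outcome, so 0.0125 in each tail.
- Evaluable number: 39 per arm with no loss; 39 × 0.95 = 37.05, so about 37 per arm after 5% loss.

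**Formula**

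The standard error is SE = √[(SD₁² + SD₂²)/n] and the noncentrality is δ = difference/SE. Power is the probability that a noncentral t variable with 2n − 2 degrees of freedom and noncentrality δ falls outside ± the critical value.

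**Reproducing the printed figures, 39 per arm** (76 df, critical t = 2.287)

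- NRS: SE = √[(580.81 + 284.60)/39] = 4.711; δ = 15.96/4.711 = 3.388; power 86.2%.
- Opioid: SE = √[(68.89 + 33.76)/39] = 1.622; δ = 6.96/1.622 = 4.290; power 97.6%.

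These round to 86% and 98%.

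**After 5% loss, 37 per arm** (72 df, critical t = 2.289)

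- NRS: SE = √(865.41/37) = 4.836; δ = 3.300; power 84.2%.
- Opioid: SE = √(102.65/37) = 1.666; δ = 4.179; power 96.9%.

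**Other methods.** The normal approximation is Φ(δ − 2.241). Each cell shows NRS / opioid power in percent.

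| Analysed per arm | t-test | Welch t | Normal approximation |
|---|---|---|---|
| 39 | 86.2 / 97.6 | 86.1 / 97.6 | 87.4 / 98.0 |
| 38 | 85.2 / 97.3 | 85.1 / 97.2 | 86.5 / 97.7 |
| 37 | 84.2 / 96.9 | 84.0 / 96.8 | 85.5 / 97.4 |

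No method in the table gives both printed figures at 37 per arm. The t-test and the Welch test give both at 39.

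**Check on the SD reading.** With equal SDs the t-test at 39 per arm gives 73.7% and 91.9%. With the treatment SD multiplied by √0.7 it gives 81.0% and 95.6%. Only the factor 0.7 reproduces the printed powers, so it is taken as the plan's assumption.

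**The case against.** The strongest reply is that a standard route reaches 39 per arm with the dropout included. By the normal approximation, 85% power for NRS needs 2(2.241 + 1.036)²/(15.96/20.80)² = 36.5, so 37 per arm, where 20.80 = √(865.41/2) is the root-mean-square SD. Then 37/0.95 = 38.9, so 39 are enrolled. Power at 37 is 85.5%, which rounds to the printed 86%. The same formula gives 97.4% for opioid use at 37, which rounds to 97% and not 98%, but that is a miss of 0.6 points on the second figure.

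Rounding of the loss also matters. Five percent of 78 is 3.9 patients. If three are lost and 38 control and 37 treated patients remain, the normal approximation gives 86.2% and 97.6%, matching both printed figures. That is a 3.8% loss (3/78), and the formula is not the test planned for the analysis.

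These routes show that the documents cannot settle how the figures were obtained. A reader might infer that the dropout was certainly left out. That goes too far: agreement to a rounded percent points to a likely method and does not prove an omission. The routes do not show that the planned t-test delivers 86% and 98% after a 5% loss.

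Two further objections stand. Patients who meet the withdrawal criteria remain in the intention-to-treat analysis, so in that analysis only missing outcomes reduce n. And the equal-SD results (NRS 73.7% at 39 per arm and 71.1% at 37; opioid 91.9% and 90.4%) concern a different assumption, which the section discloses. They are no evidence about dropout and should not be used to enlarge this point.

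**Conclusion.** The point holds as a minor reporting discrepancy. The printed 86% and 98% are what a two-sample t-test gives when all 39 per arm are analysed. With 5% of outcomes missing, the same test gives about 84% and 97%. Like for like, the loss is about 2 points for NRS (86.2% to 84.2%) and 0.7 points for opioid use (97.6% to 96.9%); as printed, it is 2 points and 1 point.

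This rests on the 0.7 factor for the treatment SD, on roughly equal loss in the two arms, and on the t-test being the test applied. That the dropout was omitted from the printed powers remains the best-fitting inference.

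A reader might go further and infer that the trial is underpowered, or that enrolment must rise to 84 so that 39 per arm stay evaluable (39/0.95 = 41.05, so 42 per arm). The documents do not support that. Power stays above 80% for both outcomes at the split 2.5% level, and the plan sets no criterion that 84% would fail.

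**What to change.** Revise the closing sentences of Number of subjects along these lines:

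> The powers of 86% and 98% assume that all 39 patients per arm are analysed (two-sample t-test, treatment-arm SD 30% lower than control). With 5% of outcomes missing (37 per arm), power is about 84% and 97%.

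If another formula produced the printed figures, name it instead and give the evaluable number per arm to which they refer. A line showing power under equal SDs is optional and is not part of this correction.

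The cost is one sentence and a slightly less favourable stated power. Enrolment, treatment and analysis do not change.
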